### **Glossary of Abbreviations**

Abbreviation	Term
DBL	DataBase Lock
SAP	Statistical Analysis Plan
TFLs	Tables, Figures and Listings

### 1. Introduction

This SAP addendum consists of derivations and mocks for the post-hoc table, figure, and listing (TFL) shells. The TFLs presented in this document are mock-ups and may be subject to minor format modifications once the actual data are used. The data represented in this document are used for example purposes only and do not reflect the actual study data captured. The overall contents in any individual TFL shell are unlikely to change, although additional tables may be added if necessary, thus changing the table number scheme. Significant changes will need be approved by Fortrea and communicated to the Sponsor.

This document should be used in conjunction with the source documents described in Section 2, and serves as providing additional information to those documents, e.g., visit windows, baseline definitions etc. are described in the SAP version 4.0, and reviewers should reference that for further information.

The database lock (DBL) occurred on 26th April 2023, the mockshells specified in this document will be produced after DBL.

### 2. Source documents

This SAP addendum was written based on the following documentation:

Document	Date	Version	
Neptuno-APL-D-003-20 SAP	21Apr2023	4.0	
Neptuno-APL-D-003-20 TFL Mock shells	21Apr2023	4.0	

### 3. TFL mock shells

For those outputs already described in the SAP and TFL mock shells version 4.0, the updates have been highlighted in red.

Characteristic Statistic	Plitidepsin 2.5mg (N=XXX)	Plitidepsin 1.5mg (N=XXX)	Control Arm (N=XXX)	Total (N=XXX)
			(	
Age (years)				
n	XXX	XXX	XXX	XXX
Mean (SD)	xx.xx (xx.xxx)	xx.xx (xx.xxx)	xx.xx (xx.xxx)	xx.xx (xx.xxx)
Median	XX.XX	xx.xx	XX.XX	XX.XX
01, 03	XX.XX, XX.XX	XX.XX, XX.XX	XX.XX, XX.XX	XX.XX, XX.XX
Min, Max	XX.X, XX.X	xx.x, xx.x	xx.x, xx.x	xx.x, xx.x
Age Group (years), n (%)				
>= 18  to  39	xxx (xxx.x)	xxx (xxx.x)	xxx (xxx.x)	xxx (xxx.x)
>= 40 to 64	xxx (xxx.x)	xxx (xxx.x)	xxx (xxx.x)	xxx (xxx.x)
>= 65	xxx (xxx.x)	xxx (xxx.x)	xxx (xxx.x)	xxx (xxx.x)
Age Group (years), n (%)				
>= 18  to  59	xxx (xxx.x)	xxx (xxx.x)	xxx (xxx.x)	xxx (xxx.x)
>= 60 to 64	xxx (xxx.x)	xxx (xxx.x)	xxx (xxx.x)	xxx (xxx.x)
>= 65 to 69	xxx (xxx.x)	xxx (xxx.x)	xxx (xxx.x)	xxx (xxx.x)
>= 70 to 74	xxx (xxx.x)	xxx (xxx.x)	XXX (XXX.X)	xxx (xxx.x)
>= 75 to 79	xxx (xxx.x)	xxx (xxx.x)	xxx (xxx.x)	xxx (xxx.x)
>= 80	xxx (xxx.x)	xxx (xxx.x)	xxx (xxx.x)	xxx (xxx.x)
Sex. n (%)				
Male	xxx (xxx.x)	xxx (xxx.x)	xxx (xxx.x)	xxx (xxx.x)
Female	xxx (xxx.x)	xxx (xxx.x)	xxx (xxx.x)	xxx (xxx.x)
		、	· · ·	~ /

#### Table 14.1.2.1.1 Post-hoc Analysis: Summary of Demographic Characteristics (Intent-To-Treat Population)

N = number of patients in analysis set; n = number of patients with data available; % = percentages are calculated based on N as the denominator.

SD = Standard deviation; Q1 =25th percentile; Q3 = 75th percentile; Min = Minimum; Max = Maximum.

[a] Only females. Percentages are calculated based on the number of females per group as the denominator.

[b] Patients with more than one race reported has been included in the Multiple category.

[c] Body mass index  $(kg/m^2) = body weight (kg) / height (m^2)$ 

[d] Body surface area  $(m^2)$  = weight 0.425 (kg) × height 0.725 (cm) × 0.007184

Reference: Listing 16.2.4.1 and 16.2.4.2

Programming notes (not part of the table):

- Table template TDM001.
- Include all parameters detailed in Table 14.1.2.1.
- The displayed xxx do not reflect actual decimal precision. Please follow Section 2.11 for rounding rules.
- A "Missing" category should only be presented under the subcategories for any categorical variable in case of missing data.

The below tables are a repeat of table 14.1.2.1.1 Post-hoc:

# Table 14.1.2.1.2 Post-hoc Analysis: Summary of Demographic Characteristics - Patients who did not Achieve a Sustained Withdrawal of Oxygen Supplementation (Intent-To-Treat Population)

• Include only patients who did not achieve a sustained withdrawal of oxygen supplementation.

## Table 14.1.2.1.3 Post-hoc Analysis: Summary of Demographic Characteristics - Patients who Achieved a Sustained Withdrawal of Oxygen Supplementation (Intent-To-Treat Population)

• Include only patients who achieved a sustained withdrawal of oxygen supplementation.

### Table 14.1.2.1.4 Post-hoc Analysis: Summary of Demographic Characteristics - Patients from Site ES40 (Intent-To-Treat Population)

• *Include only patients from site ES40.* 

### Table 14.1.2.1.5 Post-hoc Analysis: Summary of Demographic Characteristics - All Patients Except Those from Site ES40 (Intent-To-Treat Population)

#### Table 14.1.3.1.1 Post-hoc Analysis: Summary of Baseline Characteristics (Intent-To-Treat Population)

Characteristic Statistic	Plitidepsin 2.5mg (N=XXX)	Plitidepsin 1.5mg (N=XXX)	Control Arm (N=XXX)	Total (N=XXX)
Chest Imaging at Enrolment, n (%)				
Pulmonary Infiltrates	xxx (xxx.x)	xxx (xxx.x)	xxx (xxx.x)	xxx (xxx.x)
Pleural Fluid	xxx (xxx.x)	xxx (xxx.x)	xxx (xxx.x)	xxx (xxx.x)
Atelectasis	xxx (xxx.x)	xxx (xxx.x)	xxx (xxx.x)	xxx (xxx.x)
Pulmonary Oedema	xxx (xxx.x)	xxx (xxx.x)	xxx (xxx.x)	xxx (xxx.x)
Bilateral Pneumonia	xxx (xxx.x)	xxx (xxx.x)	xxx (xxx.x)	xxx (xxx.x)
Lateral Pneumonia	xxx (xxx.x)	xxx (xxx.x)	xxx (xxx.x)	xxx (xxx.x)
Other	xxx (xxx.x)	xxx (xxx.x)	xxx (xxx.x)	xxx (xxx.x)
Periods of inclusion, n (%)				
Beginning of accrual - August 2021	xxx (xxx.x)	xxx (xxx.x)	xxx (xxx.x)	xxx (xxx.x)
September 2021 - March 2022	xxx (xxx.x)	xxx (xxx.x)	xxx (xxx.x)	xxx (xxx.x)
April 2022 - End of accrual	xxx (xxx.x)	xxx (xxx.x)	xxx (xxx.x)	xxx (xxx.x)

<continue for the following characteristics: Systolic Blood Pressure (mmHg) at Screening, Diastolic Blood Pressure (mmHg) at Screening, pulse rate (beats/min) at Screening, temperature (C) at Screening, respiration rate (breaths/min) at Screening, oxygen saturation at room air (%) at Screening and FiO2 (%) at Screening>

Vaccination Status, n (%)				
Fully Vaccinated	xxx (xxx.x)	xxx (xxx.x)	xxx (xxx.x)	xxx (xxx.x)
Non-Fully Vaccinated	xxx (xxx.x)	xxx (xxx.x)	xxx (xxx.x)	xxx (xxx.x)
No Vaccinated	xxx (xxx.x)	xxx (xxx.x)	xxx (xxx.x)	xxx (xxx.x)
Fully Vaccinated+ Non-Fully	xxx (xxx.x)	xxx (xxx.x)	xxx (xxx.x)	xxx (xxx.x)
Vaccinated				

N = number of patients in analysis set; n = number of patients with data available; % = percentages are calculated based on N as the denominator. SD = Standard deviation; Q1 =25th percentile; Q3 = 75th percentile; Min = Minimum; Max = Maximum. Reference: Listing 16.2.4.2

Programming notes (not part of the table):

- Table template TDM002.
- Include all parameters detailed in Table 14.1.3.1.
- The displayed xxx do not reflect actual decimal precision. Please follow Section 2.11 for rounding rules.

• A "Missing" category should only be presented under the subcategories for any categorical variable in case of missing data.

Note: "at room air" have been removed from 'Oxygen saturation" label as it is not applicable in Tables 14.1.3.1, 14.3.5.1, 14.3.5.2 and Listing 16.2.4.2.

The below tables are a repeat of table 14.1.3.1.1 Post-hoc:

# Table 14.1.3.1.2 Post-hoc Analysis: Summary of Baseline Characteristics - Patients who did not Achieve a Sustained Withdrawal of Oxygen Supplementation (Intent-To-Treat Population)

• Include only patients who did not achieve a sustained withdrawal of oxygen supplementation.

### Table 14.1.3.1.3 Post-hoc Analysis: Summary of Baseline Characteristics – Patients who Achieved a Sustained Withdrawal of Oxygen Supplementation (Intent-To-Treat Population)

• Include only patients who achieved a sustained withdrawal of oxygen supplementation.

#### Table 14.1.3.1.4 Post-hoc Analysis: Summary of Baseline Characteristics - Patients from Site ES40 (Intent-To-Treat Population)

• *Include only patients from site ES40.* 

#### Table 14.1.3.1.5 Post-hoc Analysis: Summary of Baseline Characteristics - All Patients Except Those from Site ES40 (Intent-To-Treat Population)

The below tables are a repeat of table 14.1.3.2:

### Table 14.1.3.2.1 Post-hoc Analysis: Active Medical History by System Organ Class and Grouped Preferred Term - Patients who did not Achieve a Sustained Withdrawal of Oxygen Supplementation (Intent-To-Treat Population)

• Include only patients who did not achieve a sustained withdrawal of oxygen supplementation.

# Table 14.1.3.2.2 Post-hoc Analysis: Active Medical History by System Organ Class and Grouped Preferred Term - Patients who Achieved a Sustained Withdrawal of Oxygen Supplementation (Intent-To-Treat Population)

• Include only patients who achieved a sustained withdrawal of oxygen supplementation.

 Table 14.1.3.2.3 Post-hoc Analysis: Active Medical History by System Organ Class and Grouped Preferred Term - Patients from Site ES40 (Intent-To-Treat Population)

• Include only patients from site ES40.

# Table 14.1.3.2.4 Post-hoc Analysis: Active Medical History by System Organ Class and Grouped Preferred Term - All Patients Except Those from Site ES40 (Intent-To-Treat Population)

The below tables are a repeat of table 14.1.3.3:

 Table 14.1.3.3.1 Post-hoc Analysis: Past Medical History by System Organ Class and Grouped Preferred Term - Patients who did not Achieve a

 Sustained Withdrawal of Oxygen Supplementation (Intent-To-Treat Population)

• Include only patients who did not achieve a sustained withdrawal of oxygen supplementation.

 Table 14.1.3.3.2 Post-hoc Analysis: Past Medical History by System Organ Class and Grouped Preferred Term - Patients who Achieved a Sustained Withdrawal of Oxygen Supplementation (Intent-To-Treat Population)

• Include only patients who achieved a sustained withdrawal of oxygen supplementation.

 Table 14.1.3.3.3 Post-hoc Analysis: Past Medical History by System Organ Class and Grouped Preferred Term - Patients from Site ES40 (Intent-To-Treat Population)

• *Include only patients from site ES40.* 

 Table 14.1.3.3.4 Post-hoc Analysis: Past Medical History by System Organ Class and Grouped Preferred Term - All Patients Except Those from Site

 ES40 (Intent-To-Treat Population)

The below tables are a repeat of table 14.1.4.1:

 Table 14.1.4.1.1 Post-hoc Analysis: Summary of Prior Medications - Patients who did not Achieve a Sustained Withdrawal of Oxygen Supplementation (Intent-To-Treat Population)

• Include only patients who did not achieve a sustained withdrawal of oxygen supplementation.

 Table 14.1.4.1.2 Post-hoc Analysis: Summary of Prior Medications - Patients who Achieved a Sustained Withdrawal of Oxygen Supplementation (Intent-To-Treat Population)

• Include only patients who achieved a sustained withdrawal of oxygen supplementation.

#### Table 14.1.4.1.3 Post-hoc Analysis: Summary of Prior Medications - Patients from Site ES40 (Intent-To-Treat Population)

• Include only patients from site ES40.

### Table 14.1.4.1.4 Post-hoc Analysis: Summary of Prior Medications - All Patients Except Those from Site ES40 (Intent-To-Treat Population)

The below tables are a repeat of table 14.1.5.1:

# Table 14.1.5.1.1 Post-hoc Analysis: Summary of Signs and Symptoms - Patients who did not Achieve a Sustained Withdrawal of Oxygen Supplementation (Intent-To-Treat Population)

• Include only patients who did not achieve a sustained withdrawal of oxygen supplementation.

# Table 14.1.5.1.2 Post-hoc Analysis: Summary of Signs and Symptoms - Patients who Achieved a Sustained Withdrawal of Oxygen Supplementation (Intent-To-Treat Population)

• Include only patients who achieved a sustained withdrawal of oxygen supplementation.

### Table 14.1.5.1.3 Post-hoc Analysis: Summary of Signs and Symptoms - Patients from Site ES40 (Intent-To-Treat Population)

• Include only patients from site ES40.

### Table 14.1.5.1.4 Post-hoc Analysis: Summary of Signs and Symptoms - All Patients Except Those from Site ES40 (Intent-To-Treat Population)

The below tables are a repeat of table 14.2.3.2:

### Table 14.2.3.2.1 Post-hoc Analysis: Total Duration of Advanced Oxygen Support - Patients from Site ES40 (Full Analysis Set)

• Include only patients from site ES40.

#### Table 14.2.3.2.2 Post-hoc Analysis: Total Duration of Advanced Oxygen Support - All Patients Except Those from Site ES40 (Full Analysis Set)

The below tables are a repeat of table 14.2.3.9.1:

### Table 14.2.3.9.1.1 Post-hoc Analysis: Patients who Require High-Flow Oxygen - Patients from Site ES40 (Full Analysis Set)

- Include only patients from site ES40.
- Remove geographical region from model and footnotes because it is Not Applicable due to all patients belong to the same category.

### Table 14.2.3.9.1.2 Post-hoc Analysis: Patients who Require High-Flow Oxygen - All Patients Except Those from Site ES40 (Full Analysis Set)

The below tables are a repeat of table 14.2.3.9.2:

### Table 14.2.3.9.2.1 Post-hoc Analysis: Patients who Require High-Flow Oxygen per Period - Patients from Site ES40 (Full Analysis Set)

- Include only patients from site ES40.
- Remove geographical region from model and footnotes because it is Not Applicable due to all patients belong to the same category.

 Table 14.2.3.9.2.2 Post-hoc Analysis: Patients who Require High-Flow Oxygen per Period - All Patients Except Those from Site ES40 (Full Analysis Set)

The below tables are a repeat of table 14.2.3.10.1:

### Table 14.2.3.10.1.1 Post-hoc Analysis: Patients who Require Non-invasive Mechanical Ventilation - Patients from Site ES40 (Full Analysis Set)

- Include only patients from site ES40.
- Remove geographical region from model and footnotes because it is Not Applicable due to all patients belong to the same category.

# Table 14.2.3.10.1.2 Post-hoc Analysis: Patients who Require Non-invasive Mechanical Ventilation - All Patients Except Those from Site ES40 (Full Analysis Set)

The below tables are a repeat of table 14.2.3.10.2:

 Table 14.2.3.10.2.1 Post-hoc Analysis: Patients who Require Non-invasive Mechanical Ventilation per Period - Patients from Site ES40 (Full Analysis Set)

- Include only patients from site ES40.
- *Remove geographical region from model and footnotes because it is Not Applicable due to all patients belong to the same category.*

### Table 14.2.3.10.2.2 Post-hoc Analysis: Patients who Require Non-invasive Mechanical Ventilation per Period - All Patients Except Those from Site ES40 (Full Analysis Set)

The below tables are a repeat of table 14.2.3.11.1:

### Table 14.2.3.11.1.1 Post-hoc Analysis: Patients who Require Invasive Mechanical Ventilation or ECMO - Patients from Site ES40 (Full Analysis Set)

- Include only patients from site ES40.
- Remove geographical region from model and footnotes because it is Not Applicable due to all patients belong to the same category.

## Table 14.2.3.11.1.2 Post-hoc Analysis: Patients who Require Invasive Mechanical Ventilation or ECMO - All Patients Except Those from Site ES40 (Full Analysis Set)

The below tables are a repeat of table 14.2.3.11.2:

## Table 14.2.3.11.2.1 Post-hoc Analysis: Patients who Require Invasive Mechanical Ventilation or ECMO per Period - Patients from Site ES40 (Full Analysis Set)

- *Include only patients from site ES40.*
- Remove geographical region from model and footnotes because it is Not Applicable due to all patients belong to the same category.

### Table 14.2.3.11.2.2 Post-hoc Analysis: Patients who Require Invasive Mechanical Ventilation or ECMO per Period - All Patients Except Those from Site ES40 (Full Analysis Set)

Variable	Parameter Estimate	Standard Error	p-value	Hazard Ratio
XXXXXXXXXXXXXXXX XXXXXXXXXXXXXXXXXXXXX	X.XXXX X.XXXX X.XXXX	X.XXXX X.XXXX X.XXXX	X.XXXX X.XXXX X.XXXX	X.XXX X.XXX X.XXX

#### Table 14.2.4.1.1 Post-hoc Analysis: Time to Sustained Withdrawal of Oxygen Supplementation - Multivariate Analysis (Intent-To-Treat Population)

Notes: Sustained withdrawal of oxygen supplementation (in days) with no subsequent reutilisation during remaining study period is defined as the first day, from randomisation through completion of the study, on which a patient

i. satisfies categories 0 to 4 on the 11-point WHO Clinical Progression Scale, and

ii. has no subsequent reutilisation of oxygen supplementation (5 to 10 on the 11-point WHO Clinical Progression Scale)

If the patient is discontinued between day 15 and day 31 visits, and there is an attempt of contact and study discontinuation on or after the day 31 visit due date, the patient is censored at day 31. [a] Parameter Estimate, Standard Error, p-value, and Hazard Ratio based on a Cox proportional-hazards regression model with treatment group, randomisation stratification factors, ie, geographical region (Europe, Rest of the World), Charlson Comorbidity Index (0 - 1, > 1) and pre-baseline Barthel index (≥ 90 versus < 90) as derived using the eCRF data, and patients included before and after amendment (Protocol v.6 or before, Protocol v.7), sex (female, male), age at study entry (18 to 39, 40 to 64, ≥ 65 years), race (asian, black, white, other), ethnic group (Hispanic or Latino, Not Hispanic or Latino), site location (Site XXX, Site XXX, Other Sites), use of antiviral therapies or immunomodulatory drugs through the study (Yes, No), previous COVID-19 vaccination status (Fully vaccinated + Non-fully vaccinated, Non-fully vaccinated, Non vaccinated, Non vaccinated, anti-SARS-CoV-2 IgG at Day 1 (Non-positive, Positive), pre-randomisation dexamethasone (Yes, No), total duration of corticoid therapy (<9 days, [9-11] days, >11 days), total cumulative dose of corticoid therapy (dexamethasone or equivalent) (< 60 mg, > 60 mg), SARS-CoV-2 viral load (log10 copies/mL) at Day 1 before study drug administration (<4, [4 - 7], >7), time between onset date of COVID-19 symptoms and initiation of study treatment (≤5 days, 6 - 10 days, >10 days), body mass index (kg/m2) at Screening (< 30, ≥ 30), hypertension at Screening (Yes, No), myocardial infarction (Yes, No), congestive heart failure (Yes, No), peripheral vascular disease (Yes, No), cerebrovascular disease (Yes, No), dementia (Yes, No), chronic obstructive pulmonary disease (Yes, No), connective tissue disease (Yes, No), peptic ulcer disease (Yes, No), liver disease (None, Mild, Moderate or Severe), diabetes mellitus (None or diet controlled, Uncomplicated, End-organ damage), hemiplegia (Yes, No), moderate or severe chronic kidney disease (Yes, No), solid tumor (None, Localized, Metastatic), leukemia (Yes, No), lymphoma (Yes, No), AIDS (Yes, No), ISARIC-4C mortality score (Low (0 - 3), Intermediate (4 - 8), High (9 - 14), Very high (≥ 15)), ISARIC-4C deterioration probability ( $\leq 25$ , (25 - 50], > 50), LDH at Baseline ( $\leq ULN$ , > ULN), CRP (mg/L) at Baseline ( $\leq 100$ , > 100), D-dimer at Baseline ( $\leq ULN$ , > ULN), ferritin at Baseline ( $\leq ULN$ , > ULN), ferr ULN), creatinine at Baseline ( $\leq$  ULN,  $\geq$  ULN), IL-6 at Baseline ( $\leq$  Median,  $\geq$  Median), IL-10 at Baseline ( $\leq$  Median,  $\geq$  Median), lymphocytes count decreased at Baseline (Grade 0, Grade  $\geq$  1), neutrophils/lymphocytes ratio at Baseline ( $< 6, \geq 6$ ) and SARS-CoV-2 variant (Alpha, Beta, Gamma, Delta, Eta, Iota, Kappa, Lambda, Mu, any potential new variant) as covariates. Those covariates with more than 10% of missing values are omitted. A stepwise selection model is used, with significant level equal to 0.2 and 0.05, to enter into the model and to remain in the model, respectively.

*Programming notes (not part of the table):* 

- The displayed xxx do not reflect actual decimal precision. Please follow Section 2.11 for rounding rules.
- Omit those covariates with more than 10% of missing values from the multivariate analysis.
- Force to include the treatment arm in addition to the significant covariates.
- Remove the antiviral/immunomodulatory drug intake (no, yes), cumulative dose of corticoid therapy (≤60 mg, >60 mg) and total duration of corticoid therapy (<9 days, 9 to 11 days) variables from the modelling and the footnote.

The below tables are a repeat of table 14.2.4.1:

### Table 14.2.4.1.2 Post-hoc Analysis: Time to Sustained Withdrawal of Oxygen Supplementation - Multivariate Analysis using a Random Forest Approach (Intent-To-Treat Population)

Variable	Parameter Estimate	Standard Error	p-value	Hazard Ratio
XXXXXXXXXXXXXXXX XXXXXXXXXXXXXXXXXXXXX	X.XXXX X.XXXX X.XXXX	X.XXXX X.XXXX X.XXXX	X.XXXX X.XXXX X.XXXX	X.XXX X.XXX X.XXX

Notes: Sustained withdrawal of oxygen supplementation (in days) with no subsequent reutilisation during remaining study period is defined as the first day, from randomisation through completion of the study, on which a patient

i. satisfies categories 0 to 4 on the 11-point WHO Clinical Progression Scale, and

ii. has no subsequent reutilisation of oxygen supplementation (5 to 10 on the 11-point WHO Clinical Progression Scale)

If the patient is discontinued between day 15 and day 31 visits, and there is an attempt of contact and study discontinuation on or after the day 31 visit due date, the patient is censored at day 31. [a] Parameter Estimate, Standard Error, p-value, and Hazard Ratio based on a Cox proportional-hazards regression model with treatment group, and Baseline IL-10 (continuous) as covariates.

Programming notes (not part of the table):

- The displayed xxx do not reflect actual decimal precision. Please follow Section 2.11 for rounding rules.
- Force to include the treatment arm in addition to the covariates.

• Include the prognosis factors identified by Pharma Mar using a random forest approach as covariates in the modelling and the footnote.

Variable	Parameter Estimate	Standard Error	p-value	Hazard Ratio
XXXXXXXXXXXXXXXX XXXXXXXXXXXXXXXXXXXXX	X.XXXX X.XXXX X.XXXX	X.XXXX X.XXXX X.XXXX	X.XXXX X.XXXX X.XXXX	X.XXX X.XXX X.XXX

Table 14.2.4.2.1 Post-hoc Analysis: Time to Sustained Hospital Discharge - Multivariate Analysis (Intent-To-Treat Population)

Notes: Sustained (ie, with no subsequent readmission to Day 31) hospital discharge (in days), defined as the first day, from randomisation through completion of the study, on which a patient

i. discharges from the hospital, and

ii. has no subsequent re-admission

If the patient is discontinued between day 15 and day 31 visits, and there is an attempt of contact and study discontinuation on or after the day 31 visit due date, the patient is censored at day 31. [a] Parameter Estimate, Standard Error, p-value, and Hazard Ratio based on a Cox proportional-hazards regression model with treatment group, randomisation stratification factors, ie, geographical region (Europe, Rest of the World), Charlson Comorbidity Index (0 - 1, > 1) and pre-baseline Barthel index (> 90 versus < 90) as derived using the eCRF data, and patients included before and after amendment (Protocol v.6 or before, Protocol v.7), sex (female, male), age at study entry (18 to 39, 40 to 64, ≥ 65 years), race (asian, black, white, other), ethnic group (Hispanic or Latino, Not Hispanic or Latino), site location (Site XXX, Site XXX, Other Sites), use of antiviral therapies or immunomodulatory drugs through the study (Yes, No), previous COVID-19 vaccination status (Fully vaccinated + Non-fully vaccinated, Fully vaccinated, Non-fully vaccinated No vaccinated), anti-SARS-CoV-2 IgG at Day 1 (Non-positive, Positive), pre-randomisation dexamethasone (Yes, No), total duration of corticoid therapy (<9 days, [9-11] days, >11 days), total cumulative dose of corticoid therapy (dexamethasone or equivalent) (<60 mg, >60 mg), SARS-CoV-2 viral load (log10 copies/mL) at Day 1 before study drug administration (< 4, [4 - 7], > 7), time between onset date of COVID-19 symptoms and initiation of study treatment (< 5 days, 6 - 10 days, > 10 days), body mass index (kg/m2) at Screening (< 30, ≥ 30), hypertension at Screening (Yes, No), myocardial infarction (Yes, No), congestive heart failure (Yes, No), peripheral vascular disease (Yes, No), cerebrovascular disease (Yes, No), dementia (Yes, No), chronic obstructive pulmonary disease (Yes, No), connective tissue disease (Yes, No), peptic ulcer disease (Yes, No), liver disease (None, Mild, Moderate or Severe), diabetes mellitus (None or diet controlled, Uncomplicated, End-organ damage), hemiplegia (Yes, No), moderate or severe chronic kidney disease (Yes, No), solid tumor (None, Localized, Metastatic), leukemia (Yes, No), lymphoma (Yes, No), AIDS (Yes, No), ISARIC-4C mortality score (Low (0 - 3), Intermediate (4 - 8), High (9 - 14), Very high (≥ 15)), ISARIC-4C deterioration probability (< 25, (25 - 50], > 50), LDH at Baseline (< ULN, > ULN), CRP (mg/L) at Baseline (< 100, > 100), D-dimer at Baseline (< ULN, > ULN), ferritin at Baseline (< ULN, > 0.10), CRP (mg/L) at Baseline (< 0.10), D-dimer at Bas ULN), creatinine at Baseline ( $\leq$  ULN, > ULN), IL-6 at Baseline ( $\leq$  Median, > Median), IL-10 at Baseline ( $\leq$  Median, > Median), lymphocytes count decreased at Baseline (Grade 0, Grade  $\geq$  1), neutrophils/lymphocytes ratio at Baseline (< 6, ≥ 6) and SARS-CoV-2 variant (Alpha, Beta, Gamma, Delta, Eta, Iota, Kappa, Lambda, Mu, any potential new variant) as covariates. Those covariates with more than 10% of missing values are omitted. A stepwise selection model is used, with significant level equal to 0.2 and 0.05, to enter into the model and to remain in the model, respectively.

Programming notes (not part of the table):

- The displayed xxx do not reflect actual decimal precision. Please follow Section 2.11 for rounding rules.
- Omit those covariates with more than 10% of missing values from the multivariate analysis.
- Force to include the treatment arm in addition to the significant covariates.

• Remove the antiviral/immunomodulatory drug intake (no, yes), cumulative dose of corticoid therapy (≤60 mg, >60 mg) and total duration of corticoid therapy (<9 days, 9 to 11 days) variables from the modelling and the footnote.

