#### Statistical Analysis Plan Addendum and TFL Mock Shells Fortrea Study: 000000213894 Protocol Reference: APL-D-003-20

#### Programming notes (not part of the figure):

Type of figure	Forest Plot					
Figure Template ID Treatment display details	FG006 Display 2 tro	eatment groups per page	e. Plitidepsin 2.5mg vs	Control Arm on page 1 and Pl	itidepsin 1.5mg vs C	ontrol Arm on
X-axis label	< ( < (	Control Arm Better Control Arm Better	Plitidepsin 2.5mg Be Plitidepsin 1.5mg Be	tter> on page 1. tter> on page 2.		
X-axis Scale	0.33; 0.5; 0.	66; 1; 1.5; 2; 3.				
Y-axis label	Nil.					
Y-axis Scale	Major tick: 1 Display 2 tro	Nil>>, Minor tick: Nil. eatment groups per page	·.			
	Subgroup	Plitidepsin 2.5mg N	Control Arm N	HR [b] (95% CI)	Hazard Ratio	(on page 1)
Legend	Subgroup	Plitidepsin 1.5mg N	Control Arm N	HR [b] (95% CI)	Hazard Ratio	(on page 2)
Legend position	Тор					
Annotations Other notes	Include refer Display sub	rence line groups as following:				
	Al Cl Ga Pr Pa Se	ll patients narlson Comorbidity Inc 0 - 1 > 1 eographical Region Europe Rest of the World e-baseline Barthel index ≥ 90 < 90 stients included before a Protocol v.6 or befo Protocol v.7 x Female Male	lex c nd after amendment re			

Statistical Analysis Plan Addendum and TFL Mock Shells Fortrea Study: 000000213894 Protocol Reference: APL-D-003-20

> Age at study entry (years) 18 to 39 40 to 64  $\geq 65$ Race Asian Black White Other Ethnic group Hispanic or Latino Not Hispanic or Latino Site location: each study site with more than 1/6 out of the randomised patients (i.e. >33 randomised patients for the futility analysis and >101 randomised patients for the final analysis) will be considered as a group and the remaining study sites, i.e. those study sites with less than 1/6 out of the randomised patients will be pooled together as a one single group Site XXX Site XXX Other Sites Use of antiviral therapies or immunomodulatory drugs through the study Yes No Previous COVID-19 vaccination status Fully vaccinated Non-fully vaccinated No vaccinated Fully vaccinated + Non-fully vaccinated Anti-SARS-CoV-2 IgG Day 1 Non-positive Positive Pre-randomisation dexamethasone Yes No Total duration of corticoid therapy  $\leq 9$  days [9 11] days > 11 daysTotal cumulative dose of corticoid therapy (dexamethasone or equivalent) ≤ 60 mg

Final, Version 2.0, 12SEP2023

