- Hypertension at Screening, defined as Hypertension (Standardised MedDRA Query [SMQ]) in the Medical History form: Yes or No
- Individual co-morbidities included in the Charlson Index: myocardial infarction (Yes or No), congestive heart failure (Yes or No), peripheral vascular disease (Yes or No), cerebrovascular disease (Yes or No), dementia (Yes or No), chronic obstructive pulmonary disease (Yes or No), connective tissue disease (Yes or No), peptic ulcer disease (Yes or No), liver disease ('None', 'Mild' or 'Moderate or Severe'), diabetes mellitus ('None or diet controlled', 'Uncomplicated' or 'End-organ damage'), hemiplegia (Yes or No), moderate or severe chronic kidney disease (Yes or No), solid tumor ('None', 'Localized' or 'Metastatic'), leukemia (Yes or No), lymphoma (Yes or No) or AIDS (Yes or No).
- ISARIC-4C mortality score: Low (0 3), Intermediate (4 8), High (9 14) or Very high (≥ 15)
- ISARIC-4C deterioration probability (%): `≤ 25', `(25 50]', or `> 50'
- Lactate dehydrogenase (LDH) at Baseline: ≤ ULN or > ULN

- CRP (mg/L) at Baseline: ≤ 100 or > 100
- D-dimer at Baseline: ≤ ULN or > ULN
- Ferritin at Baseline: ≤ ULN or > ULN
- Creatinine at Baseline: ≤ ULN or > ULN
- IL-6 at Baseline: ≤ Median or > Median value (at the analysis time cutoff may be updated based on distribution values if needed)
- IL-10 at Baseline: ≤ Median or > Median value (at the analysis time cutoff may be updated based on distribution values if needed)
- Lymphocytes count decreased at Baseline: 'Grade 0' or 'Grade  $\geq 1'$
- Neutrophils/lymphocytes ratio at Baseline:  $< 6 \text{ or } \ge 6$
- SARS-CoV-2 variant: Alpha, Beta, Gamma, Delta, Eta, Iota, Kappa, Lambda, Mu, or any potential new variant

The same covariates used for the primary efficacy endpoint analysis will be used for the subgroup analyses.

For ISARIC-4C mortality score and deterioration probability calculation:

- A Glasgow coma scale score of 15 is assumed for all the patients.
- Urea (mmol/L) will be calculated as blood urea nitrogen (mmol/L) \* 60 / 28.

Forest plots of the hazard ratios, and the 95% CI for the comparison of each dose of plitidepsin versus control arm will be presented by endpoint for all subgroups using the ITT population.

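### Addendum Table 14.2.4.1.2 prints an ordinary Cox p-value for baseline IL-10, a factor the sponsor picked with a random forest, and that p-value ignores the picking

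*SAP*

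**What the plan says.** The addendum Introduction puts database lock at 26 April 2023 and states that "the mockshells specified in this document will be produced after DBL". The addendum's footer is "Final, Version 2.0, 12SEP2023".

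Table 14.2.4.1.2 of the addendum is a post-hoc multivariate analysis of the primary endpoint in the ITT population. Its programming note says "Include the prognosis factors identified by Pharma Mar using a random forest approach as covariates in the modelling and the footnote". Its footnote gives the model: "Parameter Estimate, Standard Error, p-value, and Hazard Ratio based on a Cox proportional-hazards regression model with treatment group, and Baseline IL-10 (continuous) as covariates". No candidate list, training data, tuning, hold-out sample or resampling is described. SAP v4.0, dated 21 April 2023, does not mention a random forest.

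Addendum Figure 14.2.1.2.1, the post-hoc subgroup forest plot, lists IL-10 twice: at the median, as planned, and at 3.8 ng/L. No source is given for 3.8. SAP v4.0 section 7.6.4 plans the median split and, for IL-6 and IL-10 alike, adds that "at the analysis time cutoff may be updated based on distribution values if needed".

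SAP v4.0 section 7.6.1 specifies the supportive Cox model for the primary endpoint with the three randomisation factors: region, Charlson index and pre-baseline Barthel index. The model in Table 14.2.4.1.2 has none of them.

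**The concern.** A random forest that looks for prognostic factors ranks baseline variables by how well they predict outcome. If the winner is then tested against the same outcome in the same patients, its Cox p-value answers a question about a variable fixed in advance, and this variable was not. The standard error and p-value carry no allowance for the search. The post-hoc label tells a reader when the analysis was chosen; it does not say that the p-value is calibrated for a different situation.

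At stake is the claim that IL-10 is an established predictor of oxygen withdrawal in this trial. The second IL-10 cut raises a related but conditional question. The figure prints treatment hazard ratios with 95% intervals within subgroups, and a reader cannot tell a harmless cut from one tuned to the treatment effect.

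**Working it through.** The plan gives no figure for this table, so there is none to reproduce. The check sizes the selection effect.

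**Timing.** 26 April to 12 September 2023 is 4 + 31 + 30 + 31 + 31 + 12 = 139 days, about four and a half months.

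**Number of candidates (assumed).** The forest's candidates are not given. The footnote of addendum Table 14.2.4.1.1 lists 47 covariates besides treatment, and its programming note removes three, leaving 44. A range of 10 to 44 is used.

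**Trial size (assumed).** SAP section 8 says recruitment stopped before 33% of events. 0.33 × 530 = 175 events. Section 7.6.4 equates one sixth of patients at that point with 33, so about 200 patients. SAP section 7.8 gives 116 events for one pairwise comparison.

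**Formula.** For the best of K independent candidates, none related to outcome, P(p < 0.05) = 1 − 0.95^K:

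- K = 10: 1 − 0.95^10 = 0.401
- K = 20: 1 − 0.95^20 = 0.642
- K = 44: 1 − 0.95^44 = 0.895

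**Simulation of the table's model.** 2,000 trials per setting, three arms, 201 patients, about 175 events, no treatment effect. The factor with the largest Cox score statistic was picked (a stand-in for the forest), then Cox was fitted with treatment plus that factor.

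| Candidates | True log HR of one factor, per SD | Chosen factor p < 0.05 | Median absolute log HR (as HR) | Treatment p < 0.05, two arms |
|---|---|---|---|---|
| 10 | 0 | 41% | 0.143 (1.15) | 6.0%, 6.2% |
| 44 | 0 | 89% | 0.191 (1.21) | 4.4%, 5.2% |
| 44 | 0.30 | 99% | 0.308 (1.36) | 5.1%, 4.9% |

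The first two rows agree with the formula. The treatment rejection rate stays near 5% and does not rise with the number of candidates. In the last row the true factor was picked in 89% of trials, and the median estimate is close to the assumed 0.30.

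**Simulation of the IL-10 split.** 2,000 null trials of one pair, 134 patients, about 116 events, 25 cuts between the 20th and 80th percentiles. Treatment effect within subgroups:

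| How the cut was chosen | Result under the null |
|---|---|
| Median | 6.3% per subgroup (two-sided); 5.9% favourable in either subgroup |
| Best prognostic separation | 5.6% and 5.9% per subgroup; median HR 1.00 |
| Cut and side chosen on treatment effect | 19% favourable; median HR 1.44 |

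Only the last route biases what the figure prints, and 19% should be read against 5.9%.

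**Model content.** Section 7.6.1: treatment with region, Charlson and Barthel. Table 14.2.4.1.2: treatment and IL-10. Moving from one to the other adds IL-10 and removes three factors at once, so a change in the treatment HR cannot be put down to IL-10 alone.

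**The case against.** The strongest reply is that this is one covariate in a table openly titled post-hoc, on which no step of the multiplicity procedure depends. IL-10 was not new: section 7.6.4, written before lock, lists it as a subgroup factor, and section 7.6.5 makes it a multivariate candidate. The training data are not stated, so use of the same outcomes is inferred. The 90% figure needs 44 independent, wholly null factors, whereas the listed ones overlap (Charlson with its components, ISARIC scores with age, several inflammatory markers). If IL-10 is truly prognostic, the estimate is hardly biased. As for the randomisation factors, an unstratified ITT Cox model already exists in Table 14.2.1.1.3 and is a matched comparator.

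Most of this limits the point without removing it. A planned place among many candidates does not make the winner's p-value valid. Correlation lowers the percentages but does not restore 5%. The Table 14.2.1.1.3 comparator stands, so the treatment HR is not without a reference; the addition requested is a cheap alignment with section 7.6.1.

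A reader might infer several stronger things that the documents do not support:

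- **Selection on data still open to change.** The Introduction gives a lock date, and the shell postdates it.
- **An inflated treatment HR or p-value in the IL-10 model.** The simulation shows none, and with no interaction term the table cannot show that benefit depends on IL-10.
- **Optimistic 3.8 ng/L subgroup HRs.** That holds only if the cut was tuned to the treatment effect, which is nowhere stated. The inflated p-value that a cut search gives for IL-10 itself is not printed in the figure.
- **A licence for outcome-driven cuts in section 7.6.4.** It mentions distribution only.
- **IL-10 on the raw scale.** The footnote says only that it is continuous.

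**Conclusion.** The p-value and standard error for IL-10 in addendum Table 14.2.4.1.2 do not account for its selection and should not be printed as ordinary Cox inference. Under the null, nominal 5% becomes about 40% with 10 candidates and about 90% with 44. These figures assume independent candidates, score-test selection in place of the forest, about 175 events in about 200 patients, and a forest trained on this trial's outcomes. That last assumption is the natural reading but is not stated.

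The treatment comparison in that model is not compromised, although the omission of the three randomisation factors should be corrected. For the 3.8 ng/L split, the defect is the missing origin. The 19% false-positive rate is conditional on tuning to the treatment effect, and the documents do not show that this happened.

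**What to change.** In Table 14.2.4.1.2:

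- Report the IL-10 estimate as descriptive, without a p-value, or give a confidence interval from a bootstrap that repeats the forest selection in every resample.
- Add region, Charlson and Barthel, in the form used in section 7.6.1.
- State the forest's data, candidate list, tuning and validation.

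In Figure 14.2.1.2.1, keep the planned median split as the reported IL-10 subgroup. Show the 3.8 ng/L split only if its origin is stated and did not use outcomes; otherwise drop it.

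A log2 scale for IL-10 and removal of the cut-off sentence in section 7.6.4 are optional.

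The cost is a few lines of code, some addendum wording and weaker-looking exploratory results. The primary and key secondary analyses are untouched.
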